6.1.1 Investigational drug

Eltrombopag study drug will be provided by Novartis. Sourcing of study drug by Novartis can be either through clinical supply or local commercial supply. Clinical supply will be provided globally through Global Clinical Supply and labeled as per local regulations. Local commercial supply will be sourced in the country where appropriate and as per local regulations. If eltrombopag is sourced through local commercial supply, drug will be labeled in-country and the locally approved form and packaging of eltrombopag will be used.

Eltrombopag will not be dosed by weight or body surface area.

All investigational treatment is to be stored in a secure locked area while under the responsibility of the investigator. Receipt and dispensing of investigational treatment must be recorded by an authorized person at the investigator's site.

For detailed safety information refer to the [ETB115 Investigators Brochure, current edition] and the approved product labeling. A description of the study treatment, pharmaceutical form and method of administration of eltrombopag is provided in [Table 6-2](#).

Table 6-2 Investigational drug

Study treatments	Pharmaceutical form and route of administration	Dose	Frequency and/or Regimen
Eltrombopag	Tablet for oral use	12.5 mg	Daily
Eltrombopag	Tablet for oral use	25 mg	Daily
Eltrombopag	Tablet for oral use	50 mg	Daily
Eltrombopag	Tablet for oral use	75 mg	Daily

6.1.2 Additional study treatments

No other treatment beyond investigational drug will be considered as study treatments.

6.1.3 Treatment duration

Patients may participate in the study for up to 24 months depending on their response. Patients not in sustained remission at month 12 will only be treated with eltrombopag in the study for 12 months.

Patients in sustained remission at month 12 will enter the follow-up period for an additional 12 months. Patients who relapse during the follow-up period (between months 12 and 24) will be offered retreatment with eltrombopag until the end of month 24. Some of the patients might not need retreatment with eltrombopag during the follow-up period.

Patients who receive treatment options other than eltrombopag within the follow-up period will discontinue the study at that time (see [Section 9.3](#)).

Patients may be discontinued from treatment earlier due to unacceptable toxicity at the discretion of the investigator or the patient. These patients will continue to be followed as per study design but will not be considered in having achieved sustained remission for the primary endpoint.

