6.2.3 Rescue therapy

Any ITP-directed medication or therapy, other than eltrombopag, given during the trial with the aim to increase platelet count for the patients who have clinically significant bleeding will be considered a rescue therapy and must be recorded on the appropriate CRF page. A patient who receives rescue medication or therapy will not be considered in having achieved sustained remission for the primary endpoint, unless the patient uses steroids ± IVIG as described below in the first 14 days of start of eltrombopag.

Steroids ± IVIG use as rescue medication:

In case of clinical necessities because of very low platelet count ($< 10 \times 10^9/L$) and/or significant bleeding, treatment with steroids ± IVIG and platelet transfusion is permitted together with eltrombopag for the first 14 days, calculated from the first dose day of eltrombopag.

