9.2 Study completion and post-study treatment

Study completion is defined as when the last patient finishes their end of follow-up / month 24 visit, and any repeat assessments associated with this visit have been documented and followed-up appropriately by the Investigator, or in the event of an early study termination decision, the date of that decision.

All patients who are still on study at month 12 will complete the end of treatment visit at Week 53, Day 1. Patients who are still on study treatment and not in sustained remission at month 12 will come off trial after completing the end of treatment visit. After discontinuing drug at the end of treatment visit, patients will be followed-up for safety for an additional 30 days (safety follow-up). The following data should be collected during the safety follow-up: adverse events and concomitant medications. This data can be collected via telephone/email contact or at a clinic visit (as needed).

Patients who still have sustained remission (see [Table 2-1](#)) at the end of treatment visit will enter the follow-up period for responders (see [Section 9.3](#)). The follow-up period begins after month 12.

Continuing care to study participants should be provided by the investigator and/or referring physician. The treating physician can request access to eltrombopag for patients that are continuing to benefit from treatment. Access will be dependent on the local regulatory authority approval of the product and current reimbursement options.

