1.2 Study objectives and endpoints

Table 1-1 Objectives and endpoints

Objective(s)	Endpoint(s)
Primary Objective(s)	Endpoints for primary objective(s)
Secondary Objective(s)	Endpoints for secondary objective(s)
1. To assess ability of eltrombopag to induce sustained response off treatment by month 12 in ITP patients who relapsed or failed to respond to first-line steroid treatment.	1. Proportion of patients with sustained response off treatment by month 12 where sustained response off treatment is defined as: 
 reach platelet count $\geq 100 \times 10^9/L$ (complete response [CR]) and then maintain platelet counts around $100 \times 10^9/L$ for 2 months (no counts below $70 \times 10^9/L$) AND then taper off the drug until treatment discontinuation (see Section 9.1 of the study protocol) while, maintain platelet count $\geq 30 \times 10^9/L$ in the absence of bleeding (no bleeding AEs) or use of any rescue therapy (see Section 6.2.3 of the study protocol) until month 12.
2. To assess the duration of sustained response off treatment after treatment discontinuation by month 12 and month 24	1a. Median duration of sustained response off treatment (weeks) counted from last dose of eltrombopag to month 12 for patients with sustained response off treatment 1b. Estimated median duration of sustained response off treatment (weeks) by month 24 for patients who are in sustained response off treatment at month 12 and enter 12 months follow-up period using Kaplan-Meier method 1c. Estimated median duration of sustained response off treatment (weeks) by month 24 for all patients using Kaplan-Meier method.
3. To assess the proportion of patients maintaining a sustained response off treatment after treatment discontinuation until month 24.	2. Proportion of sustained response off treatment patients at months 15, 18, 21, and 24.
4. To assess the ability of eltrombopag to induce early response by month 1	3. Number (%) of patients with platelet count $\geq 50 \times 10^9/L$ at least once by month 1 (first month) without bleeding and no rescue therapy
5. To assess the platelet count from baseline and every 3 months until month 24	4. Number (%) of patients with at least one platelet count $\geq 30 \times 10^9/L$ after eltrombopag is re-introduced, in case of loss of response ($< 30 \times 10^9/L$ and/or bleeding event) without bleeding and no rescue therapy by month 12 and 24

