2.4.2 Rescue therapy

Any ITP-directed medication or therapy, other than eltrombopag, given during the trial with the aim to increase platelet count for the patients who have clinically significant bleeding will be considered a rescue therapy and must be recorded on the appropriate CRF page (Form: Concomitant Medication, the category value at the form: Rescue medication). A patient who receives rescue medication or therapy between Step 2 and Step 3 will not be eligible for Step 3. A patient who receives rescue medication or therapy between Step 3 and Step 4 will not be eligible for Step 4. A patient who receives rescue medication or therapy will not be considered in having achieved sustained response off treatment for the primary endpoint, unless the patient uses steroids ± IVIG as described below in the first 14 days of start of eltrombopag.

Steroids ± IVIG use as rescue medication:

In case of clinical need such as very low platelet count (<10×10⁹/L) and/or significant bleeding, treatment with steroids ± IVIG and platelet transfusion is permitted together with eltrombopag for the first 14 days, calculated from the first dose day of eltrombopag. Any rescue therapy started before Day 14 may be used after Day 14 if the dose is considered low dose as per protocol definition and is being tapered down (i.e., successively lower doses after day 14).

Rescue medication will be taken from the SDTM cm.sas7bdat dataset where cmcat='RESCUE MED' for rescue therapy and exported as an EXCEL file. The clinical team will review the records captured in an Excel spreadsheet. Medications which were not considered as rescue therapy were flagged as 'Y' for the column 'NOT_RESCUE'. Per protocol, medications prior to Day 14 are not considered as rescue medication in the efficacy derivations and will be programmatically excluded. Medications that started prior to Day 14 and were still being tapered after Day 14 will also be programmatically excluded from efficacy derivations.

Once the database has locked the data will be rechecked again for any changes or new data that needs flagging.

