2.5.1 Primary endpoint

The primary endpoint is the proportion of patients with sustained response off treatment by month 12.

Sustained response off treatment is defined as:

- reach platelet count $\geq 100 \times 10^9 / L$ (CR) and then maintain platelet counts around $100 \times 10^9 / L$ for 2 months (no counts below $70 \times 10^9 / L$) **AND** then
- taper off the drug until treatment discontinuation (see Section 9.1 of the study protocol) while maintain platelet count $\geq 30 \times 10^9 / L$ in the absence of bleeding (no bleeding AEs) or use of any rescue therapy (see Section 6.2.3 of the study protocol),
- and maintain platelet count $\geq 30 \times 10^9 / L$ in the absence of bleeding (no bleeding AEs) or use of any rescue therapy (see Section 6.2.3 of the study protocol) until month 12.

In the first 12 months, the platelet count values from scheduled visits will be used, in the follow-up phase values from all visits (scheduled and unscheduled) will be used for the analysis of the platelet counts. See mapping of visits in Section 2.1.1 (Time windows).

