2.7.1 Secondary endpoints

2.7.2 Efficacy endpoint(s)

1. To assess the **duration of sustained response off treatment** after treatment discontinuation
 - 1a) Summary statistics for the duration of sustained response off treatment (weeks) counted from last dose of eltrombopag to month 12 for patients with sustained response off treatment

(SRoT_M12 patients) will be provided. Mean, SD, median, maximum, minimum, 25th percentile and 75th percentile will be provided.

1b) Kaplan-Maier analysis and corresponding plot for the duration of sustained response off treatment for all patients meeting the primary endpoint (SRoT_M12 patients) (weeks) will be provided and is counted from last dose of eltrombopag to relapse. The SRoT_M12 patients who do not relapse/ restart eltrombopag treatment until month 24 will be censored.

- Event: relapse after achieving SRoT_M12 (platelets <30 Gi/L, bleeding event, rescue therapy/platelet transfusion, or restarted eltrombopag treatment)
- Censoring rules: Patients with SRoT_M12 who enter follow-up and do not relapse by cut-off date/Month 24 will be censored at the earliest of discontinuation date/death date/M24 platelet assessment date/cutoff date. SRoT_M12 patients who did not enter or do not yet have platelet assessments in follow-up phase are censored at their M12 platelet assessment date.

1c) Kaplan-Maier analysis and corresponding plot for the duration of sustained response off treatment for all patients who achieved Step 3 (S3 patients) (weeks) will be provided and is counted from their last dose of eltrombopag on or before this last S3 to relapse.

The S3 patients who do not relapse/ restart eltrombopag treatment until month 24 will be censored.

The event and censoring rules are as in 1b) above.

It is noted that the SRoT_M12 patients are a subset of patients in the group of patients who achieved Step 3 (S3 patients).

Duration of SRoT (weeks) for the tapered patients who achieved step 3 will be summarized by SRoT_M12 status.

2. To assess the proportion of patients maintaining a sustained response off treatment after treatment discontinuation until month 24. Number (%) of patients who are in sustained response off treatment at months 15, 18, 21, and 24 will be provided.
3. To assess the ability of eltrombopag to induce **early response by month 1**

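### Duration endpoint 1b: SAP 2.7.2 censors every month-12 responder who did not enter follow-up, although entry and responder status rest on partly different rules, so the censoring may be informative

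*Protocol*

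**What the plan says.** **Entry to follow-up.** Protocol 6.1.3 states: "Patients in sustained remission at month 12 will enter the follow-up period for an additional 12 months". Protocol 9.2 ties this to Week 53 Day 1: those who still meet the Table 2-1 definition "at the end of treatment visit will enter the follow-up period for responders".

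**Responder status in the analysis.** SRoT_M12 denotes patients who meet the primary endpoint as the SAP derives it. SAP 2.5.1 says: "In the first 12 months, the platelet count values from scheduled visits will be used". SAP 2.4.2 adds a rule on rescue treatment: "Medications that started prior to Day 14 and were still being tapered after Day 14 will also be programmatically excluded from efficacy derivations". Sections 2.4.2 and 2.8.4.4 also rely on clinical-team flags for what counts as rescue and as bleeding, rechecked after database lock.

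**Population for 1b.** SAP Table 1-1 defines the endpoint "for patients who are in sustained response off treatment at month 12 and enter 12 months follow-up period", in agreement with protocol 12.5.1. SAP 2.7.2 item 1b takes all patients who meet the primary endpoint and adds: "SRoT_M12 patients who did not enter or do not yet have platelet assessments in follow-up phase are censored at their M12 platelet assessment date". Item 1c uses the same event and censoring rules. SAP Section 4 records that the description, event definition and censoring rules in 2.7.2 were updated, but does not mention the wider 1b population.

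**The concern.** A Kaplan-Meier curve treats a censored patient as having the same later relapse risk as those still followed. That is reasonable for a patient who moved away or declined further visits. It is doubtful for one who was kept out of follow-up because, under the protocol, remission had already failed.

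The 1b event is a relapse after SRoT_M12 is achieved. An occurrence before month 12 that barred entry therefore cannot become an event. Such a patient contributes event-free time up to month 12 and then leaves the risk set.

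At stake is the durability estimate. Item 2 (proportions in response at months 15 to 24) is also affected, because it has no rule for responders without follow-up data. Entry status is in addition an unused check on the primary endpoint: it was fixed by 22-Oct-2021, the last Week 53 visit, whereas the SAP history logs the detailed derivation on 26-Apr-2022.

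**Working it through.** **1. Can the two classifications differ?**

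| Element | Protocol | SAP | Possible mismatch |
|---|---|---|---|
| Counts before month 12 | 8.3.1 allows extra counts; 12.4.1 does not exclude them | 2.5.1: scheduled visits only | Responder by SAP only |
| Rescue | 6.2.3: "A patient who receives rescue medication or therapy will not be considered in having achieved sustained remission for the primary endpoint", except steroids ± IVIG in the first 14 days | 2.4.2: early rescue still tapering after Day 14 is ignored | Responder by SAP only |
| Classifying rescue and bleeding | Definitions in the text | Clinical-team flags | Either direction |
| Minimum data | 12.4.3: missing assessments disqualify | 2.5.3: at least two counts, 14 days apart | May drop a patient who had entered |
| Bleeds on Days 1 to 7 | Not exempted | 2.8.4.4 excludes them; Section 4 limits this to secondary endpoints 3, 4 and 6 | None expected: they precede tapering |

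Mismatch is possible in both directions.

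**2. The plan's own figures.** Exact binomial, null rate 0.15, alternative 0.25:
- N = 101, cut-off 22: alpha 0.0433, power 0.8042 (stated 0.043 and 0.804).
- N = 105, cut-off 23: alpha 0.0373, power 0.7995 (stated 0.037 and 0.800).

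Both are reproduced. The concern does not alter them.

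**3. Assumptions for size.** The documents give none of these:
- n = 26 responders (0.25 × 105 = 26.25).
- q = 0.30, the fraction relapsing in months 12 to 24 among those followed.
- k = 0 to 5 responders by the SAP who did not enter follow-up.

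**4. Simple bounds on the fraction still in remission at month 24.** These ignore the different off-treatment times at month 12. The censored analysis gives 1 − q = 0.70 for any k. If all k relapse, the fraction is (n − k)(1 − q)/n. If none do, it is [(n − k)(1 − q) + k]/n.

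| k | All k relapse | None relapse |
|---|---|---|
| 1 | 25 × 0.70/26 = 0.673 | (17.5 + 1)/26 = 0.712 |
| 3 | 23 × 0.70/26 = 0.619 | (16.1 + 3)/26 = 0.735 |
| 5 | 21 × 0.70/26 = 0.565 | (14.7 + 5)/26 = 0.758 |

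For k = 1 to 5 the shift is 2.7 to 13.5 points down, or 1.2 to 5.8 points up.

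**5. The Kaplan-Meier estimate itself.** Endpoint 1b runs in weeks from last dose, so the curve was simulated. Further assumptions are 4 to 32 weeks off drug at month 12 (uniform) and a constant relapse hazard. The table gives mean 52-week estimates over 4,000 runs.

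| k | All responders, non-entrants censored | Entrants only | Non-entrants as events at month 12 |
|---|---|---|---|
| 0 | 0.794 | 0.794 | 0.794 |
| 1 | 0.795 | 0.794 | 0.763 |
| 3 | 0.795 | 0.792 | 0.700 |
| 5 | 0.798 | 0.792 | 0.640 |

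Restricting to entrants moves the estimate by less than one point. Counting the k as events lowers it by about 3 points (k = 1) to 16 points (k = 5).

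A milder case gives the k patients a 60% relapse risk instead of 30%. In 1,000 runs, censoring them gave 0.792 against 0.783 with full follow-up (k = 1), 0.796 against 0.766 (k = 3), and 0.793 against 0.743 (k = 5). The overstatement is 0.9, 3.0 and 5.0 points.

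**6. Primary endpoint.** The one-sided exact p-value is 0.0373 for 23/105 and 0.0626 for 22/105. From an assumed 26 responders, losing three under the protocol definition leaves 23 and the null is still rejected; losing four leaves 22 and it is not.

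**The case against.** The strongest reply is that nothing shows a mismatched patient exists, and that the routes to one are narrow.

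- **Low unscheduled count.** The plan provides for eltrombopag to be resumed after relapse, and a resumed patient is no longer off treatment. What remains is an isolated count below 30 with no restart, bleed or rescue, and adequate counts at every scheduled visit.
- **Rescue flag.** The SAP repeats the protocol's definition of rescue, so on its face the flag is data review.
- **Steroid taper past Day 14.** This is a real rule change, but SAP Section 4 declares it, and such a patient may truly be in remission at month 12.
- **Exit at month 12.** The explicit rule in protocol 9.2 reads "Patients who are still on study treatment and not in sustained remission at month 12 will come off trial". It does not cover a patient who is off drug. Exclusion of that patient follows only from the entry rule, and the protocol does not say who judges remission at Week 53 or on which counts.
- **Existing outputs.** Planned listings already show low counts, bleeds, rescue, all assessments and disposition reasons.

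Most of this stands and limits the point. A reader might infer that SAP-only responders have in fact left the trial, but the documents give no such patient and no count. A reader might also infer that they are carried as in remission to month 24; they are right-censored at month 12 and receive no later credit. Nor does non-entry as such imply lost remission.

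The reply does not remove the discrepancy between Table 1-1 and 2.7.2, or the fact that 2.7.2 provides for non-entrants and censors them regardless of reason. Listings hold the raw material, but no planned table sets entry against responder status.

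**Conclusion.** The point holds as an inconsistency with a possible, unquantified bias. The 1b population in SAP 2.7.2 differs from protocol 12.5.1 and SAP Table 1-1, and Section 4 does not declare the change. The censoring rule is potentially informative where non-entry reflects a disqualifying low count, bleed or rescue.

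The size depends wholly on k, which is not given. With k = 0 there is no effect. Under the assumptions above, treating one to five such patients as events costs about 3 to 16 points on the 52-week estimate; if they merely relapse at twice the rate, the overstatement is about 1 to 5 points. If they are true remissions, censoring loses information and the bias may run the other way.

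It is tempting to conclude that the durability result is inflated, or that the primary result would fail. Neither is supported: the direction is unknown, and the primary conclusion changes only if enough responders fail the protocol definition to bring the count below 23.

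**What to change.** 1. Align the 1b population in SAP 2.7.2 with Table 1-1 and protocol 12.5.1 (responders who entered follow-up), or declare the wider population in SAP Section 4. This settles what is estimated. It does not itself deal with informative censoring, since the estimate barely moves.
2. Add a cross-table of SRoT_M12 by entry into follow-up, in both directions, with the reason for each mismatch. This shows whether k is zero.
3. Add a sensitivity analysis of 1b in all SRoT_M12 patients. Non-entrants with a documented count below 30, bleeding AE or rescue that disqualified them under the protocol count as events at month 12. Mismatches due only to tapering, and unrelated reasons for non-entry, stay censored.
4. Add one sensitivity analysis of the primary proportion under the protocol definition, with scheduled and unscheduled counts and the 6.2.3 rescue rule, against the cut-off of 23/105.

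The cost is a wording change, one table and two runs on collected data. The durability or primary figure may become slightly less favourable.

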6.2 Other treatment(s)

Not applicable

6.2.1 Concomitant therapy

The patient must be told to notify the investigational site about any new medications he/she takes after the start of the study treatment. All medications (other than study drug) and significant non-drug therapies (including physical therapy and herbal/natural medications) administered during the study must be listed on the Concomitant Medications or the Procedures and Significant Non-Drug Therapies electronic case report form (eCRF).

All medications, procedures and significant non-drug therapies (including physical therapy and blood transfusions) administered after the patient was enrolled into the study must be recorded on the appropriate Case Report Forms (CRF).

Each concomitant drug must be individually assessed against all exclusion criteria/prohibited medication. If in doubt the investigator should contact the Novartis medical monitor before enrolling a patient or allowing a new medication to be started. If the patient is already enrolled, contact Novartis to determine if the patient should continue participation in the study.

[figure not shown]
